10.2 SECONDARY EFFICACY PARAMETER(S)

The secondary efficacy variable is the study eye IOP at each hour evaluated.

10.2.1 Secondary Efficacy Analysis #1

The 2-sided 95% confidence interval for the mean difference in study eye time-matched IOP change from baseline between each Bimatoprost SR dose strength and timolol (Bimatoprost SR minus timolol) derived in the primary analysis will be used for secondary analysis of superiority comparison. If the upper 95% confidence limit is less than zero, the difference will be considered significant and in favor of the given Bimatoprost SR dose strength for the given timepoint.

Bimatoprost SR 15 µg (or 10 µg) will be considered superior to timolol if it demonstrates significant difference in favor of Bimatoprost SR 15 µg (or 10 µg) at each of the 6 timepoints within the 12-week period (Hours 0 and 2 at Weeks 2, 6, and 12).

10.2.2 Secondary Efficacy Analysis #2

Similarly, the superiority test of study eye IOP at each hour of a visit will be performed using the same MMRM model as described above in Section 10.1.1 with the response variable of study eye IOP.

Bimatoprost SR 15 µg (or 10 µg) will be considered superior to timolol if it demonstrates significant difference in favor of Bimatoprost SR 15 µg (or 10 µg) at each of the 6 timepoints within the 12-week period (Hours 0 and 2 at Weeks 2, 6, and 12).

10.3 EFFICACY ANALYSES FOR US FDA

10.3.1 Primary Efficacy Analysis for US FDA

For US FDA review, the primary efficacy variable will be the study eye IOP. The primary analysis will be based on Weeks 2, 6, and 12 using the ITT population. Mean IOP will be compared between each Bimatoprost SR dose strength and timolol for each hour (Hours 0 and 2) at Weeks 2, 6, and 12. Intraocular pressure measurements obtained after initiating the use of non-study IOP-lowering medication in an eye will be treated as missing for that eye.

The null and alternative hypotheses for the comparison between a given Bimatoprost SR dose strength and timolol for each hour at each visit are:

- The null hypothesis is that the difference in mean IOP between the given Bimatoprost SR dose strength and timolol (Bimatoprost SR minus timolol) is > 1.5 mm Hg.
- The alternative hypothesis is that the difference (Bimatoprost SR minus timolol) in mean IOP between the given Bimatoprost SR dose strength and timolol is ≤ 1.5 mm Hg.

Intraocular pressure will be analyzed using an MMRM approach based on the same MMRM model as described above with IOP as the response variable. The mean difference between each Bimatoprost SR dose strength and timolol and the corresponding 2-sided 95% confidence interval will be provided for each hour (Hours 0 and 2) and each visit (Weeks 2, 6, and 12).

A gatekeeping procedure will be used to control the overall type I error rate at the 0.05 level. Bimatoprost SR 15 µg will be tested against timolol first at each timepoint (Hours 0 and 2 at Weeks 2, 6, and 12) and then followed by the comparison between

Bimatoprost SR 10 µg and timolol. The test for Bimatoprost SR 10 µg versus timolol for a given hour at a visit is valid only if the noninferiority of Bimatoprost SR 15 µg to timolol has been demonstrated for the given timepoint.

Bimatoprost SR 15 µg (or 10 µg) will be declared noninferior to timolol if the upper limit of the 95% confidence interval is ≤ 1.5 mm Hg for all scheduled timepoints (Hours 0 and 2 at Weeks 2, 6, 12). Each Bimatoprost SR dose strength that shows noninferiority to timolol will be declared clinically noninferior to timolol if the upper limit of the 95% confidence interval is ≤ 1.0 mm Hg for 3 or more timepoints.

Analysis will be repeated on PP population as a sensitivity analysis. The same analysis will also be repeated with missing values imputed by time-matched LOCF and multiple imputation as sensitivity analysis (similar to Section 10.1.1).

10.3.2 Secondary Efficacy Analysis for US FDA

For each Bimatoprost SR dose strength which demonstrates efficacy (clinical noninferiority) as described in the primary efficacy analyses for US FDA, the secondary efficacy analysis is to test the superiority of the Bimatoprost SR dose strength versus timolol.

For the superiority test of study eye IOP at each hour of a visit, the null hypothesis is that there is no difference between a given Bimatoprost SR dose strength and timolol. The alternative hypothesis is that there is a difference. The null hypothesis will be tested using the same MMRM model as described for the primary efficacy analysis for US FDA. A 2-sided 95% confidence interval for the mean difference in study eye IOP between each Bimatoprost SR dose strength and timolol (Bimatoprost SR minus timolol) will be provided. If the upper 95% confidence limit is less than zero, the difference will be considered significant and in favor of the given Bimatoprost SR dose strength for the given timepoint.

The following gatekeeping procedure will be applied to control the overall type I error rate at the 0.05 level for the US FDA primary and secondary hypotheses sequentially.

1. Bimatoprost SR 15 µg is noninferior to timolol at all six time points using a non-inferiority margin of 1.5 mmHg.
2. Bimatoprost SR 10 µg is noninferior to timolol at all six time points using a non-inferiority margin of 1.5 mmHg.
3. Bimatoprost SR 15 µg is superior to timolol at all 6 timepoints.
4. Bimatoprost SR 10 µg is superior to timolol at all 6 timepoints.

The above hypotheses will be tested in a sequential order. If at any step a test fails, the test procedure will stop and no further hypotheses will be tested. Following the above testing sequence, if Bimatoprost SR 10 µg demonstrates noninferiority to timolol at all six time points using a non-inferiority margin of 1.5 mm Hg, Bimatoprost SR 15 µg will be tested for superiority and considered statistically superior to timolol, if it shows statistically significant difference in favor of Bimatoprost SR 15 µg at all 6 time points (Hours 0 and 2 at Weeks 2, 6, and 12). A similar criterion for claiming superiority of Bimatoprost SR 10 µg over timolol will be employed.

[REDACTED]

[REDACTED]

[REDACTED]

[REDACTED]

[REDACTED]

[REDACTED]

[REDACTED]

[REDACTED]

[REDACTED]

[REDACTED]

[REDACTED]

[REDACTED]

[REDACTED]

[REDACTED]

[REDACTED]

[REDACTED]

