7.6 Analyses for US FDA

Primary Efficacy Analyses

For the US FDA review, the primary efficacy variable will be the study eye IOP. The primary analysis will be based on Weeks 2, 6, and 12 using the ITT population. Mean IOP will be compared between each Bimatoprost SR dose strength and timolol for each hour (Hours 0 and 2) at Weeks 2, 6, and 12.

The null and alternative hypotheses for the comparison between a given Bimatoprost SR dose strength and timolol for each hour at each visit are:

- The null hypothesis is that the difference in mean IOP between the given Bimatoprost SR dose strength and timolol (Bimatoprost SR minus timolol) is > 1.5 mm Hg.
- The alternative hypothesis is that the difference (Bimatoprost SR minus timolol) in mean IOP between the given Bimatoprost SR dose strength and timolol is ≤ 1.5 mm Hg.

IOP will be analyzed using an MMRM approach based on the same model as described in Section 7.3.1. Within the framework of this model, the mean difference between each Bimatoprost SR dose strength and timolol and the corresponding 2-sided 95% confidence interval will be provided for each hour (Hours 0 and 2) and each visit (Weeks 2, 6, and 12). A gatekeeping procedure will be used to control the overall type I error rate at the 0.05 level at each timepoint, testing Bimatoprost SR 15 μ g against timolol first and followed by the comparison between Bimatoprost SR 10 μ g and timolol. The test for Bimatoprost SR 10 μ g versus timolol for a given hour at a visit is valid only if the noninferiority of Bimatoprost SR 15 μ g to timolol has been demonstrated for the given timepoint.

Each Bimatoprost SR dose strength that shows noninferiority to timolol at all 6 timepoints with a 1.5 mm Hg margin (ie, the upper limit of the 95% confidence interval is ≤ 1.5 mm Hg) will be declared clinically noninferior to timolol if the upper limit of the 95% confidence interval is ≤ 1.0 mm Hg for 3 or more timepoints.

Sensitivity analyses of handling missing data will be performed using multiple imputation.

Secondary Efficacy Analyses

For each Bimatoprost SR dose strength which demonstrates efficacy (clinical noninferiority) as described in the primary efficacy analyses, secondary efficacy analyses comparing the Bimatoprost SR dose strength and timolol to test the no-difference null hypothesis will be

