performed at scheduled visits (Weeks 2, 6, and 12) and hours for IOP. A gatekeeping procedure will be used to control the overall type I error rate at the 0.05 level within each dose strength; the specific sequence of the tests will be provided in the analysis plan.

[REDACTED]

[REDACTED]

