16.7.2 Incomplete Stop Date

The following rules will be applied to impute the missing numeric fields for an incomplete prior or concomitant medication stop date unless the stop date is marked as ongoing. If the imputed stop date is before the start date (imputed or nonimputed start date), the imputed stop date will be equal to the start date. If the stop date is marked as ongoing, the study exit date will be assigned to the missing fields. If the study exit date is not available, the last visit date will be used for imputation.

Missing Month and Day

- If the year of the incomplete stop date is the same as the year of the study exit date, the month and day of the study exit date will be assigned to the missing fields.
- If the year of the incomplete stop date is before the year of the study exit date, *December 31* will be assigned to the missing fields.
- If the year of the incomplete stop date is after the year of the study exit date, *January 1* will be assigned to the missing fields.

Missing Month Only

- If only the month is missing, the day will be treated as missing and both the month and the day will be replaced according to the above procedure.

Missing Day Only

- If the month and year of the incomplete stop date are the same as the month and year of the study exit date, the day of the study exit date will be assigned to the missing day.
- If either the year of the incomplete stop date is before the year of the study exit date or if both years are the same but the month of the incomplete stop date is before the month of the study exit date, the last day of the month will be assigned to the missing day.
- If either the year of the incomplete stop date is after the year of the study exit date or if both years are the same but the month of the incomplete stop date is after the month of the study exit date, the first day of the month will be assigned to the missing day.

17.0 **CHANGES TO ANALYSES SPECIFIED IN PROTOCOL**

Two additional terms the time-matched baseline IOP (either Hour 0 or Hour 2 according to the response variable) and timepoint-by-baseline Hour 0 IOP interaction were added to the primary efficacy analysis model, but were not presented in protocol amendment 2, dated 16MAR2017.

18.0 **REFERENCES**

19.0 **AMENDMENTS**

19.1 **AMENDMENT 1**

[figure not shown]

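### Does SAP 10.3.2 leave two conflicting rules for when superiority over timolol is tested in the US FDA analysis?

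*SAP*

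**What the plan says.** Protocol 7.6 introduces the US secondary analysis dose by dose: "For each Bimatoprost SR dose strength which demonstrates efficacy (clinical noninferiority) as described in the primary efficacy analyses, secondary efficacy analyses comparing" each such dose with timolol. On error control it says: "A gatekeeping procedure will be used to control the overall type I error rate at the 0.05 level within each dose strength". It leaves the order open: "the specific sequence of the tests will be provided in the analysis plan".

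SAP 10.3.2 starts with the same entry condition: "For each Bimatoprost SR dose strength which demonstrates efficacy (clinical noninferiority) as described in the primary efficacy analyses for US FDA". It then introduces a gatekeeping procedure "to control the overall type I error rate at the 0.05 level for the US FDA primary and secondary hypotheses sequentially". The procedure has four steps:

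1. 15 µg noninferior at all six timepoints, margin 1.5 mm Hg
2. 10 µg noninferior at all six timepoints, margin 1.5 mm Hg
3. 15 µg superior at all six timepoints
4. 10 µg superior at all six timepoints

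The stopping rule follows: "If at any step a test fails, the test procedure will stop and no further hypotheses will be tested". The section adds that 15 µg is tested for superiority once 10 µg has shown noninferiority at the 1.5 margin.

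SAP 17.0, which lists departures from the protocol, mentions only two covariate terms that "were added to the primary efficacy analysis model, but were not presented in protocol amendment 2, dated 16MAR2017".

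**The concern.** Read alone, the opening sentence and Protocol 7.6 give each dose its own route to a superiority test once that dose is clinically noninferior. The sequence ties the doses together: 15 µg superiority waits on 10 µg noninferiority, and 10 µg superiority waits on 15 µg superiority. The SAP has no sentence saying that the sequence overrides the opening one, and Section 17.0 does not note the move from control within a dose to control across doses.

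If both rules were live, the same data could allow a US superiority claim under one and forbid it under the other, and the choice might be made after unmasking. The rules also differ in error control. With separate routes, the chance of at least one false superiority claim across the two doses can exceed one-sided 2.5%.

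**Working it through.** **Inputs** (SAP 14.0, Protocol 7.7): 180 per group, SD 4.0 mm Hg, within-subject correlation 0.6, six timepoints. Differences from timolol for 10 µg are −0.25 (Weeks 2 and 6) and 0 (Week 12). The 15 µg dose is 0.25 better throughout, so −0.50 and −0.25.

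**Half-width of each 95% interval:** t(0.975, 358 df) × SD × √(2/n) = 1.967 × 4.0 × √(2/180) = 0.83 mm Hg.

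**Thresholds for the observed difference:**
- 1.5 margin: at most 1.5 − 0.83 = 0.67
- 1.0 margin: at most 1.0 − 0.83 = 0.17
- superiority: below −0.83

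**Reproducing the stated power.** Simulation with a shared timolol arm gives clinical noninferiority power of 95.2% for 15 µg. For 10 µg it gives 81.8% when 15 µg must also be noninferior at the 1.5 margin. The plan states 95% and 81%.

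**Can the opening condition change what the sequence claims?** Clinical noninferiority in SAP 10.3.1 needs an upper limit of at most 1.5 at all six timepoints and at most 1.0 at three or more. Superiority needs an upper limit below 0 at all six. Since 0 < 1.0 < 1.5, superiority implies clinical noninferiority of that dose. For 10 µg, SAP 10.3.1 also requires 15 µg noninferiority, which step 1 has already secured. Adding the opening condition to the sequence therefore removes no claim, and none was removed in any simulated trial. In 1.2% of trials the sequence reaches step 3 although 15 µg is not clinically noninferior, but no superiority claim can arise there.

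**Does the sequence meet the protocol's error requirement?** Each step needs success at all six timepoints using the upper limit of a 95% interval, so it has one-sided level at most 2.5%. Testing in fixed order with a stop keeps the chance of any false claim among the four at or below 2.5%. The hypotheses for one dose are a subset of the four, so control within each dose follows.

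**How far would a per-dose reading differ?** At the planning effects:

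| | 15 µg | 10 µg |
|---|---|---|
| Dose clinically noninferior, superiority step not reached | about 9.3% | about 80% |
| Final superiority claim differs | 0.006% | 0.18% |

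The first row counts tests not run. The 80% is nearly the 81.8% of trials in which 10 µg is clinically noninferior, less the roughly 1.6% in which 15 µg is superior: 81.8 − 1.6 = 80.2.

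**Larger effects, assumed for illustration** (constant over visits; the documents plan none of them):
- −1.25 (15 µg) and −1.0 (10 µg): the chance of a 10 µg claim is 32.7% per dose and 25.8% under the sequence, a difference of 6.9 points.
- −1.5 (15 µg) and 0 (10 µg), a gap six times the planned one: the chance of a 15 µg claim is 81.7% per dose and 70.7% under the sequence.

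**One-sided chance of any false superiority claim.** In the worst case (zero true difference at one timepoint, strong benefit at the other five) it is 4.5 to 4.7% under the per-dose reading and about 2.4 to 2.5% under the sequence. With no true difference anywhere it is about 0.14% and 0.07%.

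**The case for a change.** The strongest case for a change is that the protocol delegated the order of the tests but fixed their scope as within each dose, and says superiority testing will be done for each clinically noninferior dose. Under the sequence such a dose may go untested. That is a departure, Section 17.0 omits it, and a confirmatory claim should not depend on which sentence a reader prefers. The wording would cost almost nothing to tidy.

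Part of this stands. The opening sentence does not point to the sequence, and Section 17.0 could have recorded that one sequence spans both doses. The charge of two competing rules does not stand. The opening sentence sets no order, significance level or stopping point, so it cannot serve as a testing procedure. Anyone who tested a dose on that sentence alone, after an earlier step had failed, would break an explicit instruction in the same section. The doses were also never independent in the protocol: Protocol 7.6 already makes the 10 µg noninferiority test depend on 15 µg at each timepoint. The sequence is stricter than the protocol's requirement and satisfies it.

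**Conclusion.** No change follows. An analyst who follows SAP 10.3.2 as written runs the four steps in order and stops at the first failure. The resulting superiority claims are the same whether or not the clinical noninferiority condition is also imposed. That equivalence follows from the ordering of the margins and does not depend on the simulation assumptions. The error rate is held at one-sided 2.5% across both doses, so the 4.5 to 4.7% figure belongs to a reading that the stopping rule excludes.

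The comparison with a per-dose reading does rest on assumptions: 180 evaluable patients per group, SD 4.0, equal correlation of 0.6 and complete data. At the planning effects, final claims would differ in 0.006% (15 µg) and 0.18% (10 µg) of trials. The larger differences need effects beyond those planned, and the lost claims are the price of controlling error across doses, which is a fair trade. A cross-reference in the opening sentence or a line in Section 17.0 would be harmless, but it would alter no test, claim or number. The point is confined to US secondary superiority claims.

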11.0 SAFETY ANALYSES

The safety analysis will be performed using the safety population. The safety parameters will include the following nonocular safety parameters: nonocular AEs, clinical laboratory values, vital signs, and pregnancy; [REDACTED]

[REDACTED] Unless otherwise stated, the last nonmissing safety assessment before the first dose of study treatment will be used as the baseline for all analyses of that safety parameter. Continuous variables will be summarized by number of patients and mean, SD, median, the 1st quartile and the 3rd quartile, minimum, and maximum values. Categorical variables will be summarized by number and percentage of patients.

[REDACTED]

For all safety by-cycle summary analyses, in order to compare cycles of similar duration, the data included in each cycle will be,

- Cycle 1 (16 weeks): data from the 1st injection to the 2nd injection date -1 or upper bound of week 15 visit window (section 16.1) if a patient didn't receive the 2nd injection;
- Cycle 2 (16 weeks): data from the 2nd injection to the 3rd injection date -1 or upper bound of week 31 visit window (section 16.1) if a patient didn't receive the 3rd injection;
- Cycle 3 (20 weeks): data from the 3rd injection to upper bound of week 52 visit window (section 16.1);
- Extended safety follow up: data after week 52 for patients with 3 injections and extended follow up.

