Bimatoprost SR 10 µg	Dose strength: 10 µg	Sham administration procedure
	Eye drops: Vehicle BID	Eye drops: Timolol BID
Bimatoprost SR 15 µg	Dose strength: 15 µg	Sham administration procedure
	Eye drops: Vehicle BID	Eye drops: Timolol BID
Control	Sham administration procedure	Sham administration procedure
	Eye drops: Timolol BID	Eye drops: Timolol BID

BID = twice daily

The patients will begin self-administration of the study-provided eye drops (vehicle or timolol) in both eyes, starting with the evening dose on the first administration (Bimatoprost SR or Sham administration) day visit. Patients will continue self-administration of the study-provided eye drops in the morning (08:00 ± 1 hour) and in the evening (20:00 ± 1 hour) approximately 12 hours apart throughout the study, with the exception of the morning of a subsequent visit, on which the morning eye drop administration will be performed at the study site.

Randomization/Stratification: Randomization to treatment groups will use a 1:1:1 ratio (Bimatoprost SR 10 µg:Bimatoprost SR 15 µg:Control). Randomization will be stratified by baseline study eye Hour 0 IOP (≤ 25 mm Hg or > 25 mm Hg).

Visit Schedule: Patients who complete the entire study without receiving nonstudy IOP-lowering medication in both eyes will have a minimum of 25 visits and 6 phone calls. [REDACTED]

[REDACTED]

Patients who have not received nonstudy IOP-lowering medication (prohibited prior to Week 52) in both eyes will receive a repeat administration of Bimatoprost SR (or Sham administration in Control group study eyes and all fellow eyes) at the Week 16 and Week 32 visits as indicated. Administration should not occur if the investigator believes that there are any safety concerns. Patients who have received nonstudy IOP-lowering medication in both eyes will be followed for at least 12 months following the last administration of Bimatoprost SR or Sham, at which time they may exit early at the investigator’s discretion.

Study Population Characteristics

Number of Patients: Approximately 600 patients will be enrolled in the study.

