8.9 Withdrawal Criteria

After the first administration (or Sham), failure to undergo an Administration Day visit does not indicate total withdrawal from the study. Patients who have received nonstudy IOP-lowering medication in only one eye will continue through the duration of the study. Patients who have received nonstudy IOP-lowering medication in both eyes, or patients who do not undergo Cycle 2 or 3 (or both) Administration Visits, will still be followed for 12 months after the last Bimatoprost SR or Sham administration for safety reasons. These patients are eligible for Early Discontinuation (Early Exit) as described in Section 8.8, above.

The investigator should consider withdrawing a patient from the study early if any of the following criteria are met:

- Patient develops (or has an exacerbation of) a medical condition that, in the opinion of the investigator, compromises the patient's ability to participate in the study
- Patient develops (or has an exacerbation of) a medical condition that, in the opinion of the investigator, compromises the patient's ability to participate in the study
- Patient is unwilling or unable to continue to comply with study procedures
- Patient is unwilling or unable to continue in the study

If a patient develops (or has an exacerbation of) a medical condition that, in the opinion of the investigator, would put the patient at an unacceptable medical risk by continuing study participation, the patient will be withdrawn from the study.

Whenever possible, the decision to withdraw a patient from the study or study treatment should be discussed with Allergan.

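### SAP 11.0 opens safety cycles by injection count but closes them at fixed visits, which breaks the by-cycle summaries for a patient who misses Week 16 and is administered at Week 32

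*SAP*

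**What the plan says.** SAP 11.0 states the scope and purpose of the rule: "For all safety by-cycle summary analyses, in order to compare cycles of similar duration, the data included in each cycle will be". The windows are then:

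- **Cycle 1:** "Cycle 1 (16 weeks): data from the 1st injection to the 2nd injection date -1 or upper bound of week 15 visit window", the second limit applying when no 2nd injection was received.
- **Cycle 2, also labelled 16 weeks:** "data from the 2nd injection to the 3rd injection date -1 or upper bound of week 31 visit window (section 16.1"), the second limit applying when no 3rd injection was received.
- **Cycle 3:** "Cycle 3 (20 weeks): data from the 3rd injection to upper bound of week 52 visit window (section 16.1").
- **After Cycle 3:** "Extended safety follow up: data after week 52 for patients with 3 injections and extended follow up".

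SAP 11.1 gives a separate by-cycle rule for treatment-emergent adverse events (TEAEs). An event belongs to a cycle if it starts from that cycle's administration onward and before the next cycle's administration. No calendar week closes the cycle.

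The protocol schedules administrations on Day 1, Week 16 and Week 32 (Section 5.6). A skipped one is anticipated. The Protocol Summary says "Administration should not occur if the investigator believes that there are any safety concerns". Section 8.9 says that missing an administration visit is not withdrawal, and that "patients who do not undergo Cycle 2 or 3 (or both) Administration Visits, will still be followed for 12 months" after their last administration.

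**The concern.** The start of a cycle is an ordinal (which injection this is for the patient), while its fallback end is a place on the calendar. The two agree only if no administration is skipped before a later one. Section 8.9 lists missing Cycle 2, Cycle 3 or both as distinct possibilities, so missing Cycle 2 alone leaves a Week 32 administration visit to attend.

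The study objective covers safety after initial and repeated administration, and Protocol 7.3.4 promises adverse event tables by treatment cycle. A patient whose Week 16 administration was withheld, and who was administered again at Week 32, contributes to the repeat-administration picture. The by-cycle tables should have a clear place for that patient. As written they do not, and two programmers working from 11.0 and 11.1 could place the same event differently.

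**Working it through.** **Inputs.** Administrations at Weeks 0, 16 and 32 (Protocol 5.6). Cycle rules and labels of 16, 16 and 20 weeks (SAP 11.0). The visit-window table in SAP 16.1 is redacted, so the upper bounds of the Week 15 and Week 31 windows, U15 and U31, are assumptions. U31 is varied from Week 31.0 (no allowance) to Week 34.5 (midpoint of the Week 31 and Week 38 visits). The 16-week label implies about Week 32.

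**1. The plan's own figures, all three administrations on schedule.**

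- Cycle 1 = 16 − 0 = 16 weeks
- Cycle 2 = 32 − 16 = 16 weeks
- Cycle 3 = 52 − 32 = 20 weeks

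These match the labels.

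**2. Week 32 missed, administrations at Weeks 0 and 16.** Cycle 2 = U31 − 16, or 15 to 18.5 weeks over the assumed range. The fallback works here.

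**3. Week 16 missed, administrations at Weeks 0 and 32, counting injections literally.**

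- The 2nd injection is at Week 32, so Cycle 1 = 32 − 0 = 32 weeks (224 days), twice its label. The Week 15 fallback is not triggered, because a 2nd injection exists.
- There is no 3rd injection, so Cycle 2 = U31 − 32.
- Cycle 3 and extended follow-up both require a 3rd injection, so the patient has neither.
- Time from Week 32 to Week 52 in no cycle = 52 − max(32, U31).

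| Assumed U31 | Cycle 2 length | Weeks 32–52 in no cycle |
|---|---|---|
| Week 31.0, no allowance | −7 days | 20 weeks |
| Day before Week 32 | −1 day | 20 weeks |
| Week 32, implied by the label | 0 days | 20 weeks |
| Week 32.5, midpoint of Weeks 31 and 34 | +3.5 days | 19.5 weeks |
| Week 34.5, midpoint of Weeks 31 and 38 | +17.5 days | 17.5 weeks |

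Everything after Week 52 is also outside any category, for every value of U31.

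**4. The same patient under the SAP 11.1 rule.** Events after Week 32 stay with that administration, since nothing closes the cycle. Cycle 1 still reaches Week 32, because no administration intervenes. So 11.1 differs from 11.0 on the second administration and does not shorten Cycle 1. By-cycle summaries of safety data other than TEAEs have only 11.0 to follow.

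**5. The same patient with cycles numbered by schedule.** Cycle 1 = 0 to U15 (about 16 weeks by the label). There is no Cycle 2. Cycle 3 = 52 − 32 = 20 weeks. The gap in no cycle is 32 − U15, about 16 weeks by the label (13.5 to 17 weeks for U15 from Week 18.5 down to Week 15).

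**The case against.** **The data are not lost.** A reader might infer that the second administration's safety data disappear. They do not. SAP 11.0 governs only by-cycle summaries. Under SAP 11.1 any event starting on or after first treatment is a TEAE for the study treatment period and enters the whole-study tables. SAP 16.3 uses all post-baseline assessments for safety evaluation and lists them. This stands, and it limits the point to the by-cycle tables.

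**SAP 11.1 already handles adverse events.** Its rule would keep events after Week 32, and 11.1 also tabulates ocular TEAEs within and beyond 2 days of each cycle's administration. It is therefore not established that early events after the Week 32 administration leave the adverse event tables. But 11.0 claims all by-cycle safety summaries, so the two rules conflict and no order of precedence is given.

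**The ordinals may mean scheduled slots.** Protocol Section 3 describes the second and third administrations as scheduled ones at 16 and 32 weeks, and SAP 7.0 treats cycles as slots. On that reading the Week 32 administration opens Cycle 3 and most of the anomaly goes. However, the condition of 3 injections for extended follow-up points to a count. Taken as written, it excludes this patient's data after Week 52 on either reading.

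**The scenario is inferred.** No visible text describes administration at Week 32 after a missed Week 16, Protocol 5.10 speaks of fixed 16-week intervals, and the visit procedures are redacted. Equally, no visible text rules it out, and Section 8.9 implies it. Study eyes on nonstudy IOP-lowering medication are a different case: they receive Sham at later administrations, and SAP 9.1 counts Sham, so their sequence need not break.

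**Direction of bias.** A reader might infer that the rule makes repeat dosing look safer, because Cycle 1 gains time and Cycle 2 loses it. The documents give no event rates and no count of such patients. Events in Weeks 16 to 32 do follow only the first administration, so putting them in Cycle 1 lengthens its window without assigning them to the wrong implant. No direction is shown.

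**Conclusion.** The point holds for the by-cycle safety summaries. Read as an injection count, SAP 11.0 gives a patient administered on Day 1 and at Week 32 a 32-week Cycle 1, a Cycle 2 of roughly zero length, no Cycle 3 and no extended follow-up. That defeats its stated aim of cycles of similar duration. Over the assumed bounds, 17.5 to 20 of the 20 weeks to Week 52, and all later data, fall in no cycle. For TEAEs this conflicts with SAP 11.1.

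The result rests on three things: the count reading, which the text favours but does not state; an assumed Week 31 bound; and the occurrence of such patients, whose number the documents do not give. Purely as an illustration, 1%, 3% or 5% of 200 per group would be 2, 6 or 10 patients per group. The tables affected are descriptive, and no efficacy test is touched. The correction is worth making because the plan foresees the skipped visit and the repair is cheap.

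**What to change.** In SAP 11.0, define cycles by scheduled administration:

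- **Cycle 1:** from the Day 1 administration to the day before the Week 16 administration, or to the Week 15 upper bound if Week 16 was not given.
- **Cycle 2:** from the Week 16 administration to the day before the Week 32 administration, or to the Week 31 upper bound if Week 32 was not given. It is empty if Week 16 was not given.
- **Cycle 3:** from the Week 32 administration to the Week 52 upper bound, whether or not Week 16 was given.
- **Extended follow-up:** after Week 52, for every patient administered at Week 32, with a flag for two versus three administrations.

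Use the same windows in the by-cycle TEAE rule of SAP 11.1, so that one rule governs.

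The cost is SAP wording and a small change to the cycle derivation from administration dates. Patients dosed on schedule keep 16, 16 and 20 weeks. There are two downsides to disclose. Cycle 3 will hold a few patients on their second administration, which the flag identifies. A skipped patient's data from the Week 15 bound to Week 32 will sit in no cycle; show them as a separate interval, or state that they appear only in the whole-study tables.
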